#### c) Outcome Measures Pertaining to Each Aim

- *Aim 1:* To compare efficacy of ILTAC-10, ILTAC-20, and ILTAC-40 versus placebo, we will measure the change from baseline in pain, objective and subjective markers of inflammation, physical functioning, and lesion size as well as comparing these changes among the different treatment groups. Change from pain baseline will be quantified by comparison of the NRS pain scale across different treatment groups (Appendix B). Objective markers of inflammation include c-reactive protein (CRP), erythrocyte sedimentation rate (ESR), and interleukin-6 (IL-6), which will be obtained from chart review of standard of care initial, 2 week, and 4 week follow-up HS visit. Erythema and edema will be measured clinically based on a 5-point ordinal scale (Appendix E). Suppuration will be measured on a dichotomous scale, by the presence or absence of purulent drainage from the lesion. Physical functioning will be measured by change from baseline in the Patient-Reported Outcomes Measurement Information System (PROMIS) measure of physical functioning. Separate forms will be administered for adult and pediatric participants. A one point change, either positive (improvement) or negative (decline), will be considered clinically meaningful (Appendix F and Appendix G). Lesion size will be measured in centimeters at baseline and during the week 2 and 4 visit.

- *Aim 2:* Side effects of ILTAC-10, ILTAC-20, and ILTAC-40 that will be investigated include thinning/atrophy of the skin, acneiform lesions, capillary dilations, and dyschromia. Hypothalamic-pituitary-adrenal (HPA) axis suppression will be obtained through chart review of standard of care serum 8 AM cortisol and ACTH levels at week 2 and 4 follow-up HS visits. Self-evaluations will be conducted by the patient and documented via telephone interviews. Clinical-evaluations will be conducted at the follow-up visits.
- *Aim 3:* To measure the patient's satisfaction after treatment, we will compare the results from the satisfaction survey between the different treatment groups at baseline, day 2, day 6, week 2, and week 4. The patient satisfaction survey will address disease control, and response to injection (in terms of pain, drainage, and lesion size), and quality of life (Appendix D).

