##### *Secondary Outcomes*

- Change from baseline in NRS pain scale at days 2, 6, and 14.
- Difference in change from baseline in NRS pain scale at days 2, 6, 14, and 28 between ILTAC-10, ILTAC-20, ILTAC-40.
- Change from baseline in HS-PGA score at week 2 and 4.
- Difference in change from baseline in HS-PGA score at week 2 and 4 between ILTAC-10, ILTAC-20, ILTAC-40.
- Change from baseline in objective markers of inflammation (c-reactive protein [CRP], erythrocyte sedimentation rate [ESR], and interleukin-6 [IL-6]) at week 2 and 4.

- Change from baseline in subjective markers of inflammation (erythema, edema, and suppuration) at week 2 and 4.
- Change from baseline in lesion size at week 2 and 4.
- Difference in change from baseline in lesion size at week 2 and 4 between ILTAC-10, ILTAC-20, ILTAC-40.
- Change from baseline in Patient-Reported Outcomes Measurement Information System (PROMIS) measure of physical functioning at days 2, 6, 14, and 28.
- Difference in change from baseline in PROMIS at days 2, 6, 14, and 28 between ILTAC-10, ILTAC-20, ILTAC-40.
- Proportion of subjects reporting side effects at days 2, 6, 14, and 28.
- Difference in proportion of subjects reporting side effects at days 2, 6, 14, and 28 between ILTAC-10, ILTAC-20, ILTAC-40.
- Baseline patient satisfaction.
- Change from baseline in patient satisfaction at days 2, 6, 14, and 28.
- Serum cortisol and ACTH levels at week 2 and 4.
- Change in serum cortisol and ACTH levels from week 2 to 4.

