## 7.0 DATA ANALYSIS

- a) Statistical Methods  
We will analyze the data from the study using an intention to treat approach. Categorical variables, including presence of side effects, drainage, and physical function, will be analyzed with chi square tests. Continuous variables, such as NRS pain scale, markers of inflammation, and lesion size, will be analyzed by T-test. Sensitivity analyses or exploratory analyses may be performed to examine the effect difference for race or gender. In the unlikely case patients do not receive the treatment they will still be randomized for analysis using a per protocol approach. All statistical tests will be 2-sided, with  $p < 0.05$  considered significant.
- b) There will be no interim analysis or early stopping of the study.
- c) Confounding and effect modification will be addressed by randomization of the subjects and blinding of both the investigators and the participants.
- d) If subjects are lost to follow up, they will be analyzed in the group to which they were initially randomized.

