## Appendix E: Ordinal Scale to Grade Erythema and Edema

Visual assessment ordinal scale to grade skin erythema

- 0, no erythema
- 1, very faint erythema: skin has a very light pink color
- 2, faint erythema, skin reaction is more apparent with clear borders but is still pink with more intensity
- 3, bright erythema, erythema is apparent in bright pink and borders are clearly defined
- 4, skin is bright red, borders are very well defined, capillaries and bruising may be visible

Assessment ordinal scale to grade edema

- 0, no edema (soft)
- 1, moderate to severe edema (soft to hard)
- 2, fluctuant

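### Edema is said to be graded on a 5-point scale, but Appendix E gives it three codes, with no mild grade, moderate and severe merged, and fluctuance as the top code

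*Combined protocol and SAP*

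**What the plan says.** Under Aim 1 in Section 2.0 c), the plan describes one type of scale for both signs: "Erythema and edema will be measured clinically based on a 5-point ordinal scale (Appendix E").

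Appendix E then gives two lists of different length. The erythema list runs from 0 up to "4, skin is bright red, borders are very well defined, capillaries and bruising may be visible". The edema list starts at "0, no edema (soft"), continues with "1, moderate to severe edema (soft to hard"), and ends at code 2, fluctuant. No other edema scale appears in the document.

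The scale feeds a listed secondary outcome: "Change from baseline in subjective markers of inflammation (erythema, edema, and suppuration) at week 2 and 4". Section 7.0 a) gives the only test that could cover these grades: "Continuous variables, such as NRS pain scale, markers of inflammation, and lesion size, will be analyzed by T-test". The categorical variables that it names for chi-square tests are side effects, drainage and physical function. Erythema and edema are not among them.

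**The concern.** The text and the appendix disagree on how many edema levels exist, and changing the number in the text would not cure the problem. A three-code scale that goes from no edema directly to moderate or severe edema leaves the assessor without a rule for mild edema, and it cannot separate moderate from severe.

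The plan itself makes edema matter. Section 1.0 cites reduced edema as a documented effect of the injections and criticises the earlier randomized trial for not addressing markers of inflammation. The Hypothesis section expects a dose-dependent response across three concentrations. A scale with almost no gradation of swelling is poorly suited to showing a gradient. Grades that are merged or forced at the time of assessment cannot be recovered from the recorded codes afterwards.

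**Working it through.** **Inputs.** Stated number of points: 5 (Section 2.0 c, Aim 1). Coded levels: Appendix E. Outcome: change from baseline at weeks 2 and 4 (Secondary Outcomes). Analysis: Section 7.0 a).

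**Step 1: count the levels.** Levels = highest code − lowest code + 1, since the codes are consecutive.

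| Sign | Codes | Levels | Stated | Agrees? | Largest possible change |
|---|---|---|---|---|---|
| Erythema | 0 to 4 | 4 − 0 + 1 = 5 | 5 | yes | 4 − 0 = 4 |
| Edema | 0 to 2 | 2 − 0 + 1 = 3 | 5 | no | 2 − 0 = 2 |

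The stated figure is reproduced for erythema only.

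**Step 2: map degrees of swelling to the edema codes.** For a non-fluctuant lesion: none → 0; mild → no code; moderate → 1; severe → 1. A fluctuant lesion is coded 2, with no reference to how swollen it is.

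**Step 3: work out the change scores** (follow-up code − baseline code; negative is improvement).

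| Course of the lesion | Change score |
|---|---|
| Severe to moderate | 1 − 1 = 0 |
| Severe to mild | 0 − 1 = −1 if mild is coded 0; 1 − 1 = 0 if coded 1 |
| Mild to none | 0 − 0 = 0 if mild is coded 0; 0 − 1 = −1 if coded 1 |
| Severe to none | 0 − 1 = −1 |
| Fluctuant to non-fluctuant, still severely swollen | 1 − 2 = −1 |

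The first row is lost whatever the rater does. The second and third rows depend on an unwritten rule. The last two rows receive the same score for very different results. A non-fluctuant lesion starting at code 1 can register improvement only by moving to 0. Such lesions are within the entry criteria, which require an inflamed nodule or an abscess.

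**Step 4: check the reach.** The primary outcome is NRS pain at week 4, and Table 1 is built on pain. Its first row (ρ = 0.1) gives SD of change = √(1 + 1 − 2 × 0.1) = √1.8 = 1.342. With 30 per arm, a difference of 1 and two-sided alpha 0.05, the two-sample t-test has power 0.8102 against the tabulated 0.81021. That row reproduces and does not involve the edema scale.

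**Step 5: read Section 7.0 against the outcome list.** If its markers of inflammation include the subjective ones, a three-code item goes to a t-test as though continuous. If they mean only CRP, ESR and IL-6, edema and erythema have no stated test. Either reading leaves a line to be written.

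**The case against.** The best defence is that this is a small inconsistency on a minor item. Edema is one of three signs in one secondary outcome, and no separate between-dose comparison is listed for it, unlike pain, HS-PGA, lesion size and PROMIS. Lesion size in centimetres captures some local response. The assessor is to be trained on the subjective markers. This stands as a limit on the impact, but training cannot supply a missing grade and lesion size does not replace an edema grade.

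Four stronger readings might be inferred, and the documents do not support them.

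- *The scale misses the most likely response.* The plan gives no baseline distribution of edema and no expected pattern of change. Only severe-to-moderate improvement is certain to be lost; severe-to-mild is recorded if the rater codes mild as 0.
- *Every mild case is wrong by a full grade.* Mild lies between codes 0 and 1 and has no correct code from which to be a full grade away. The supportable statement is that its coding is undefined.
- *Edema will certainly be analysed by t-test.* Section 7.0 says "markers of inflammation, and lesion size, will be analyzed by T-test", but the outcome list separates objective from subjective markers, Section 2.0 c) calls the edema scale ordinal, and drainage goes to chi-square. The laboratory markers alone may be meant.
- *The order of the codes is shown to be invalid.* Section 1.0 describes nodules that may progress to fluctuant abscesses, so the sequence can be read as lesion progression. What can be said is that code 2 names a different feature from the amount of swelling, so the scale mixes two things.

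Loss of a level when the PDF was read cannot be excluded, but the codes 0, 1, 2 run without a gap and the erythema list beside them is complete.

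**Conclusion.** The inconsistency is established, and it goes beyond a clerical slip. Five points are stated and three are defined for edema, and following the appendix as written yields change scores that are partly lost and partly rater-dependent. It should be corrected before the scale is used.

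The consequence is bounded: two of the intended five levels are absent (5 − 3 = 2), and the largest change is 2 points where a five-level scale would allow 4. The effect on the comparison between arms cannot be quantified, because the share of lesions that are mild, moderate, severe or fluctuant is not given. The conclusion rests on Appendix E being complete as read and on its being the only edema scale in use.

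**What to change.** Before first use:

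1. In Appendix E, give edema an ordinal scale with a written anchor for each grade and with none, mild, moderate and severe kept separate. Record fluctuance as its own yes/no item.
2. In Section 2.0 c), state the number of points for erythema and for edema separately, so that each matches the appendix. A fifth edema level is not required: nothing in the documents supports splitting mild from very mild, and an unanchored split could add rater variability.
3. In Section 7.0 a), say that erythema and edema grades at weeks 2 and 4 are analysed by an ordinal method, either proportional odds with baseline grade in the model or a Wilcoxon test, and make clear which markers of inflammation the t-test covers.

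The minimum alternative, correcting the text to three levels and adding a rule for coding mild edema, would remove the contradiction and the rater's discretion. It would still merge moderate with severe and keep fluctuance on the same scale.

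The cost is one appendix edit, a little assessor training on the revised grades within training already planned, and one sentence of analysis text. The sample size and visit schedule do not change.

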### 3.0 STUDY POPULATION

- a) Study Population: The study population includes patients >13 years old with HS by a physician. All patients with HS-PGA greater than 2 will be included, regardless of comorbidities.
- b) Sample Size/Power Calculation: The primary outcome of our trial is a reduction in pain measures before and after treatment. We will have 4 groups: normal saline, ILTAC-10, ILTAC-20, and ILTAC-40. Of importance, these ILTAC doses are currently used for HS flares and are standard treatment for other dermatologic conditions, such as keloids. To estimate the sample size needed in each arm, we assumed that the pain score in our patients is normally distributed. The mean difference in pain score between normal saline and ILTAC-10 is estimated to be 1, with a standard deviation of 1, at baseline and also two days later, as is consistent with our clinical experience. We also assumed a range of correlations (0.1-0.9) that may be observed for a patient's pain score at the multiple follow-up points. When comparing normal saline and ILTAC-10, the most conservative of the treatment arms in terms of pain change, it is shown that at least 30 participants per arm are required to detect the anticipated effects (see Table 1 below for power calculations). Additionally, given that we expect to see a greater reduction in pain with ILTAC-20 and ILTAC-40, we will be more than sufficiently powered to detect the large pain reductions anticipated in the ILTAC-20 and ILTAC-40 groups. This conservative approach allows for the detection of a clinically meaningful change, as any substantial reduction in pain would result in clinical utilization of ILTAC.

**Table 1.** Tests for Two Groups of Pre-Post Scores. Numeric Results for Comparing Mean Change in a Repeated Measures Design. Null Hypothesis:  $\delta = 0$ . Alternative Hypothesis:  $\delta \neq 0$ . Results assuming a t-test.

| Target Power | Actual Power | N1 | N2 | N  | $\delta$ | $\sigma(T1)$ | $\sigma(T2)$ | $\rho$ | $\sigma(Diff)$ | Alpha |
|--------------|--------------|----|----|----|----------|--------------|--------------|--------|----------------|-------|
| 0.8          | 0.81021      | 30 | 30 | 60 | 1        | 1            | 1            | 0.1    | 1.342          | 0.05  |
| 0.8          | 0.81347      | 27 | 27 | 54 | 1        | 1            | 1            | 0.2    | 1.265          | 0.05  |
| 0.8          | 0.8004       | 23 | 23 | 46 | 1        | 1            | 1            | 0.3    | 1.183          | 0.05  |
| 0.8          | 0.80321      | 20 | 20 | 40 | 1        | 1            | 1            | 0.4    | 1.095          | 0.05  |
| 0.8          | 0.80704      | 17 | 17 | 34 | 1        | 1            | 1            | 0.5    | 1              | 0.05  |
| 0.8          | 0.81254      | 14 | 14 | 28 | 1        | 1            | 1            | 0.6    | 0.894          | 0.05  |
| 0.8          | 0.82111      | 11 | 11 | 22 | 1        | 1            | 1            | 0.7    | 0.775          | 0.05  |
| 0.8          | 0.83633      | 8  | 8  | 16 | 1        | 1            | 1            | 0.8    | 0.632          | 0.05  |
| 0.8          | 0.87068      | 5  | 5  | 10 | 1        | 1            | 1            | 0.9    | 0.447          | 0.05  |

- Report Definitions
  - i. Target Power is the desired power value (or values) entered in the procedure. Power is the probability of rejecting a false null hypothesis. Actual power is the power obtained in this scenario. Because N1 and N2 are discrete, this value is often (slightly) larger than the target power. N1 and N2 are the number of items sampled from each population. N is the total sample size,  $N1 + N2$ .  $\delta$  is mean change of group 2 minus the mean change of group 1 assuming the alternative hypothesis.  $\sigma(T1)$  and  $\sigma(T2)$  are the standard deviations of measurements at time 1 and time 2, respectively.  $\rho$  is correlation between a pair of observations made on the same subject.  $\sigma(Diff)$  is the standard deviation of the paired differences, assumed equal for the two groups. Alpha is the probability of rejecting a true null hypothesis.
- Summary Statements
  - i. A 2-by-2 repeated measures design consists of two groups of subjects, each measured at two time points. In this case, the primary goal of the study is to compare the change across time in group 1 to the change across time in group 2. Sample sizes of 30 in group 1 and 30 in group 2 achieve 81% power to detect a difference in mean changes of 1.0 with a standard deviation of 1.0 at the first time point, a standard deviation of 1.0 at the second time point, and a correlation between measurement pairs of 0.100. The significance level (alpha) is 0.050 using a two-sided, two-sample t-test.
- c) Inclusion Criteria
  - Age > 13 years old.
  - Subject must voluntarily sign and date an informed consent, approved by an independent ethics committee / institutional review board.
  - Subject is willing to comply with the procedures in this protocol.

- The subject must be diagnosed with HS and receiving care at HSC
- Subjects with Hidradenitis Suppurativa Physician Global Assessment (HS-PGA) score between 2 and 5 (Appendix A).
- The subject must have an inflamed nodule or abscess at the time of enrollment.

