## 2.0 STUDY DESIGN

### a) Study Design

[figure not shown]
A double-blinded, randomized, placebo-controlled study examining the relative efficacy of ILTAC-10, ILTAC-20, and ILTAC-40 versus placebo for acute flares of HS in subjects with moderate to severe HS.

The duration of the study will be approximately 4 weeks for each enrolled patient and will include an initial screening/randomization/treatment visit and a 4-week follow-up period.

During the initial visit, subjects who meet the study's eligibility criteria will be randomized to receive either ILTAC-10, ILTAC-20, ILTAC-40, or normal saline (NS) placebo in a 1:1:1:1 ratio. The volume of ILTAC or NS administered is calculated based on the largest dimension of the HS lesion, which is measured by its greatest width in mm. For example, if a lesion is irregular in shape, measuring 22mm by 18mm, 22mm will be the largest dimension used for calculating volume. The administered volume (ml) is scaled by increments of 0.2ml, which corresponds to the HS lesion size, and ranges from 0.2ml to 2.0ml. The maximum volume of either ILTAC-10, ILTAC-20, ILTAC-40 or NS administered to any given HS lesion is 2.0ml.

**Figure 1.** Hidradenitis Suppurativa Lesion Size and Volume of administration of ILTAC-10, ILTAC-20, ILTAC-40, or normal saline placebo.

| HS lesion size (cm) | Volume (ml) |
|---------------------|-------------|
| 0.0 – 0.49          | 0.2         |
| 0.5 – 0.99          | 0.4         |
| 1.0 – 1.49          | 0.6         |
| 1.5 – 1.99          | 0.8         |
| 2.0 – 2.49          | 1.0         |
| 2.5 – 2.99          | 1.2         |
| 3.0 – 3.49          | 1.4         |
| 3.5 – 3.99          | 1.6         |
| 4.0 – 4.49          | 1.8         |
| 4.5 – 5.0           | 2.0         |

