#### Target population and recruitment methods

The target population will include patients over the age of 13 receiving care at the HSC for mild to advanced HS disease experiencing an acute flare. Patients will be recruited by the PI and study personnel (recruitment strategies are detailed in section 4).

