#### Inclusion Criteria

- Age > 13 years old.
- Subject must voluntarily sign and date an informed consent, approved by an independent ethics committee / institutional review board.
- Subject is willing to comply with the procedures in this protocol.
- The subject must be diagnosed with HS and receiving care at HSC
- Subjects with Hidradenitis Suppurativa Physician Global Assessment (HS-PGA) score between 2 and 5 (Appendix A).
- The subject must have an inflamed nodule or abscess at the time of enrollment.

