#### Exclusion Criteria

- The subject has an HS-PGA score of 0 or 1
- The subject has received ILTAC less than 8 days prior to the initial visit.
- The subject does not have capacity to consent to the study.
- The subject has taken systemic steroids at least 4 weeks prior to the time of enrollment.
- The subject has a known allergy or history of adverse reaction to steroids.
- The subject is pregnant.
- Subjects who have received a biologic therapy two weeks before and during the study period.

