## 10.0 APPENDICES

### Appendix A: HS-PGA Score

Disease severity, measured by HS-PGA, is defined as follows:

- 0, clear
- 1, minimal: noninflammatory nodules
- 2, mild: fewer than 5 inflammatory nodules or 1 abscess/draining fistula with no inflammatory nodules
- 3, moderate: 5 or more inflammatory nodules, or 1 abscess/draining fistula and at least 1 inflammatory nodule, or 2 to 5 abscesses/draining fistulas and fewer than 10 inflammatory nodules
- 4, severe: 2 to 5 abscesses/draining fistulas and at least 10 inflammatory nodules
- 5, very severe: more than 5 abscesses/draining fistulas

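### The criteria lists admit HS-PGA grade 2 (mild), but section 3.0 a) and the design statement describe a population without it, so they misstate whom the result applies to.

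*Combined protocol and SAP*

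**What the plan says.** The protocol states the severity of the intended patients in several places.

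- **Inclusion Criteria (section 2.0 a, repeated in 3.0 c):** "Subjects with Hidradenitis Suppurativa Physician Global Assessment (HS-PGA) score between 2 and 5".
- **Exclusion Criteria (both sections):** the only severity exclusion is "The subject has an HS-PGA score of 0 or 1".
- **Target population and recruitment methods (section 2.0):** patients with "mild to advanced HS disease experiencing an acute flare".
- **Study Population (section 3.0 a):** "All patients with HS-PGA greater than 2 will be included, regardless of comorbidities".
- **Study Design (section 2.0 a):** the comparison with placebo is "for acute flares of HS in subjects with moderate to severe HS".
- **Appendix A:** the grade in dispute is "2, mild: fewer than 5 inflammatory nodules" (with an alternative definition by one abscess or draining fistula). Grade 3 is moderate, 4 severe and 5 very severe.

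Two further places bear on which text governs. The entry for Visit 1 in section 2.0 b) has eligibility assessed against the criteria in 2.0 a). Section 4.0 pre-selects candidates on the inclusion and exclusion criteria.

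On analysis, section 7.0 a) plans t-tests for continuous outcomes, including NRS pain, and names only race and gender for possible exploratory work. Section 7.0 c) leaves confounding to randomization and blinding. The randomization section describes 1:1:1:1 allocation and mentions no stratification by severity.

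**The concern.** The criteria and two descriptions of the population disagree on whether mild disease belongs in the trial. A design statement and a study population paragraph are the texts that a report usually carries forward. If patients are enrolled on the criteria lists and the report uses the wording of 2.0 a) or 3.0 a), a result from a mixed sample will be presented as a result for moderate or worse disease.

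The planned analysis would not reveal this. The comparison is unadjusted, severity is not a named factor, and no display by baseline grade is planned. The cut-off also matters for a secondary outcome, change in HS-PGA at weeks 2 and 4, because a patient's starting grade limits how far the score can fall.

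**Working it through.** **1. Convert each statement to HS-PGA grades, using Appendix A.**

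| Place | Statement, in short | Grades implied |
|---|---|---|
| Inclusion Criteria, 2.0 a) and 3.0 c) | 2 to 5 | 2, 3, 4, 5 |
| Exclusion Criteria, 2.0 a) and 3.0 | 0 and 1 out | 2, 3, 4, 5 remain |
| Target population, 2.0 | mild upwards | from 2 |
| Study Population, 3.0 a) | above 2 | 3, 4, 5 |
| Study Design, 2.0 a) | moderate to severe | from 3 (literally 3 and 4; grade 5 is not named) |

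**2. Take the difference.** {2, 3, 4, 5} less {3, 4, 5} = {2}. The criteria and section 3.0 a) differ by exactly the mild grade.

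**3. Try the reading that might remove the conflict.** Suppose the inclusion range excludes its end points. It then becomes {3, 4}. That drops grade 5, which section 3.0 a) includes. It also leaves grade 2 neither included nor listed as an exclusion, and still contradicts the target population, which starts at mild. No reading makes all the statements agree.

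**4. Ask which text governs enrolment.** The Visit 1 entry points to the criteria in 2.0 a), and section 4.0 agrees. Grade 2 patients are therefore eligible in practice. What remains wrong is the description of the population.

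**5. Check whether the sample size depends on the cut-off.** Section 3.0 b) uses a difference in mean change of 1, SD 1 at both times, correlation 0.1, 30 per arm and two-sided alpha 0.05.

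- SD of change = √(1 + 1 − 2 × 0.1) = √1.8 = 1.342, as in Table 1.
- Noncentrality = 1 / (1.342 × √(2/30)) = 2.887, with 2 × 30 − 2 = 58 degrees of freedom.
- Power from the noncentral t distribution = 0.81021, equal to the first row of Table 1. The other eight rows also reproduce.

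HS-PGA enters none of these inputs, and no effect or SD is given by severity. Table 1 is the same whichever range is chosen.

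**6. See what the cut-off does change.** HS-PGA has a floor of 0. A grade 2 patient can improve by at most 2 − 0 = 2 points, while grades 3 to 5 can improve by 3 to 5 points. The possible range of the secondary HS-PGA outcome therefore depends on whether grade 2 is admitted. This shows that the population definition matters; it does not show a bias between randomized arms.

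**The case against.** The strongest reply is that the plan already says which text decides. Eligibility is assessed against the criteria in 2.0 a), those criteria are consistent wherever they appear, and the target population paragraph agrees with them. Section 3.0 a) says that patients above grade 2 will be included; it does not instruct anyone to turn grade 2 away. The design statement does not mention HS-PGA and may be only a loose description. The aims and hypothesis speak of acute flares with no severity limit.

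Most of this stands. It answers the inference that enrolment itself is undetermined, or that sites would refuse mild patients. It does not make the two descriptions correct: section 3.0 a) is where the study population is defined, and it gives a numerical threshold different from the criteria.

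A reader might draw other, stronger inferences that the documents do not support:

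- **Mild patients have less room for pain to fall, so the 1-point planning effect is at risk.** HS-PGA counts lesions and NRS is patient-reported pain. Every participant must have an inflamed nodule or abscess, and no pain data by grade are given.
- **A particular number of patients falls outside the described population.** The documents give no severity mix, so any count would be a guess.
- **The remark on comorbidities contradicts the exclusions.** Section 1.0 uses that word for cardiovascular, endocrine, gastrointestinal and psychiatric disorders, and the exclusion lists name none of these.

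It can also be said that a covariate goes further than a wording mismatch requires. That is fair as to necessity: adjustment is an inexpensive improvement if grade 2 is kept, and is not needed to resolve the contradiction.

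**Conclusion.** The inconsistency is real but limited. Under the governing criteria, grade 2 patients will be enrolled. Section 3.0 a) and the design statement in 2.0 a) describe a population without them, and so misstate whom the result applies to. The size is one severity grade out of the four that the criteria admit; the number of patients and any effect on pain, its SD or power cannot be obtained from the documents. The stated power of 0.81021 is unaffected.

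The conclusion rests on reading the design statement's severity terms on the Appendix A scale. If that statement is set aside as informal, the numerical conflict between section 3.0 a) and the criteria lists remains.

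**What to change.** The sponsor should choose one HS-PGA range and reconcile the design statement, the target population paragraph, both inclusion lists, both exclusion lists and section 3.0 a) to it. Which range is intended is the sponsor's decision. If the criteria lists stand, only the sentences in 2.0 a) and 3.0 a) need rewording, to grade 2 or above and to mild through very severe disease.

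If grade 2 is kept, two additions to section 7.0 a) are worthwhile:

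- Compare week-4 change in NRS pain between arms in a linear model that includes baseline HS-PGA, in place of the unadjusted t-test. This deals with chance imbalance in severity, since no stratification is described. The gain in precision cannot be stated in advance, because the relation of HS-PGA to pain change is not given.
- Show the week-4 results for grade 2 and for grades 3 to 5 descriptively, without tests. With 30 per arm, dividing an arm leaves fewer than 30 in each part, below what Table 1 requires at its planning correlation of 0.1.

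The cost is two wording edits and a short analysis amendment before unblinding. Baseline HS-PGA is already recorded at enrolment (study calendar, section 5.0 f), so no data collection is added. The downside is a change of primary model; entered as a single term, the covariate takes one degree of freedom, from 58 to 57 in a two-arm comparison of 30 each.
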